6. EFFICACY ANALYSES

6.1. General Considerations

The primary analysis set for efficacy analyses will be the FAS, defined in Section 3.1.2.

Efficacy analysis will generally be conducted on the following 2 datasets:

- 1) On-treatment data as specified in Section 3.8.2 with exclusion of the observations described as the following. This is the primary analysis dataset for efficacy analysis.
 - For subjects who continued study drug BUT did not achieve at least 20% improvement from Baseline in both SJC66 and TJC68 at
 - Nominal Week 14 visit, then efficacy data collected after nominal Week 14 visit will be excluded from the primary analysis, OR
 - Nominal Week 12 visit if subjects missed Week 14 visit or the response status cannot be determined due to missing SJC66 or TJC68 value at Week 14, then efficacy data collected after nominal Week 16 visit will be excluded from the primary analysis, OR
 - Nominal Week 16 visit if subjects missed both Week 12 and Week 14 visits or the response status cannot be determined due to missing SJC66 or TJC68 value at both Week 12 and Week 14 visits, then efficacy data collected after nominal Week 16 visit will be excluded from the primary analysis

If subjects missed all three visits (Week 12, Week 14 and Week 16) or the response status cannot be determined at all of these three visits, all the efficacy data collected will be included for analysis

 - Subjects who continued on study drug will be evaluated for loss of therapeutic response from nominal Week 30 visit through nominal Week 52 visit. For subjects who failed to maintain at least a 20% improvement from Baseline in SJC66 and TJC68 (which is confirmed at 2 consecutive visits, and a missed visit will not count against them), efficacy data collected after the second consecutive visit will be excluded from the primary analyses.
- 2) All available data (including data collected under standard of care).

Estimands:

Two efficacy estimands, composite estimand and treatment policy estimand are defined for the primary and key secondary efficacy endpoints, respectively.

The **Composite Estimand** is defined as following. This is the primary estimand for efficacy endpoints.

- 1) Population: Subjects in the FAS.
- 2) Variable: Primary and key secondary endpoints as well as some other secondary endpoints (see details in Section 6.2, 6.3 and 6.4)
- 3) Intercurrent events: The following intercurrent events are taken into account:
 - If a subject takes standard of care medications due to inadequate response or discontinues from study treatment, treat data as missing from the point of inadequate response or study drug discontinuation (ie, on-treatment data defined above).
 - If a subject discontinues from the study, treat data as missing from the point of loss to follow-up onward.
- 4) Population-level summary: proportion difference for binary efficacy endpoints or mean difference in change from baseline for continuous efficacy endpoints between each filgotinib group and placebo group or adalimumab group if applicable.

The **Treatment-Policy Estimand** is defined as following. This is the secondary estimand for efficacy endpoints.

- 1) Population: Subjects in the FAS.
- 2) Variable: Primary and key secondary endpoints as well as some other secondary endpoints (see details in Section 6.2, 6.3 and 6.4)
- 3) Intercurrent events: The occurrence of an intercurrent event is irrelevant. All observed values will be used regardless of occurrence of an intercurrent event.
 - All observed values will be used regardless of occurrence of an intercurrent event (ie, All available data defined above).
 - If a subject discontinues from the study, treat data as missing from the point of loss to follow-up onward.
- 4) Population-level summary: Proportion difference for binary efficacy endpoint or mean difference in change from baseline for continuous efficacy endpoints between each filgotinib group and placebo group or adalimumab group if applicable.

The other secondary endpoints specified in both estimands include ACR50, ACR70, and the individual components of the ACR response.

To handle the missing data caused by the intercurrent events, the following analyses will be performed for both estimands:

- For binary endpoints, missing data will be treated as non-responder for the primary analysis. Sensitivity analyses including observed data only, last observation carry forward (LOCF), multiple imputation, and tipping point methods will be applied.
- For continuous endpoints, missing data will be handled using a mixed-effects model for the primary analysis. Sensitivity analyses, including using multiple imputation and tipping point methods, will be applied.

In addition, analyses will be performed for the primary and key secondary endpoints by replacing the population in both estimands with the Per-Protocol analysis set as defined in Section 3.1.3. For these analyses, the binary missing data will be imputed as non-responder and the continuous missing data will be handled using a mixed-effects model.

Selection of Efficacy Data in the Event of Multiple Records in an Analysis Visit Window

If multiple valid, nonmissing efficacy measurements exist in an analysis window, records will be chosen based on the following rules if a single value is needed:

- The record closest to the nominal day for that visit will be selected
- If there are 2 records that are equidistant from the nominal day, or more than 1 record (with time known) on the selected day, the latest record will be taken
- If chronological order cannot be determined (eg, more than 1 record on the same day with time missing), for any given subject, the worst outcome will be selected.

Calculation of Composite Endpoints

For the calculation of composite endpoints including DAS28(CRP), ACR20/50/70, ACR-N, SDAI, and CDAI, we use the following steps unless otherwise specified:

- Step 1: Assign individual components to analysis visit windows defined in Section 3.8.2
- Step 2: Within each analysis visit window, select the component-level data based on the rules for selecting efficacy data as above
- Step 3: Calculate the composite endpoint based on the selected component-level data in Step 2.

Missing Data Imputation

Below are the descriptions for the imputation methods that will be used throughout the efficacy analyses:

- Observed case (OC): Missing values remain missing. For the categorical composite endpoints, in the case that some components are missing, the composite endpoint assessment will be derived based on the non-missing components. If non-missing components are not sufficient to determine final composite endpoint, then the composite endpoint will be set as missing. For continuous composite endpoints (including ACR-N), if any components are missing, the composite endpoints will be set as missing.
- Last observation carried forward (LOCF): Baseline measurements will not be carried forward to postbaseline. Only postbaseline measurements will be LOCF. For the composite endpoints, the last nonmissing postbaseline observation will be carried forward to subsequent visits for each individual component first, and then calculate the composite endpoints using individual components imputed by LOCF as described above. If a subject does not have a nonmissing observed record for a postbaseline visit, the last postbaseline record prior to the missed visit will be used for this postbaseline visit. If the last nonmissing observation prior to the missing visits cannot be determined due to multiple measurements occurring at the same time or the time not available within the same day, the worst outcome will be used for LOCF. If missing components still exist after LOCF, the composite endpoints will be calculated using the same rules as described in OC.
- Non-responder imputation (NRI): For all binary response measurements, starting from OC, all missings will be set as non-responders.

If a subject only has baseline measurements, LOCF and OC analyses will not include this subject. But this subject will be treated as non-responder in NRI analyses.

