All subjects will be evaluated for loss of therapeutic response from Week 30 through the Week 52 study visit. Subjects failing to maintain at least a 20% improvement from Day 1 in TJC and SJC (as confirmed at 2 consecutive visits) will discontinue investigational therapy but will continue with study visits and assessments. All subjects who discontinue from investigational therapy are to receive standard of care treatment for their RA as determined by the investigator.

Subjects who have received at least one dose of study drug and choose to prematurely terminate study participation for any reason should complete an ET visit at the time of study discontinuation, as well as a post dosing visit four weeks after the last dose of study drug (post treatment Week 4) regardless of dosing duration.

At completion of the 52-week treatment period, subjects (who did not discontinue assigned study drug or have not met criteria for loss of therapeutic response) will be provided the option to enter a Long Term Extension (LTE) study (GS-US-417-0304).

[figure not shown]
Subjects or trained caregivers will self-administer the adalimumab (or adalimumab placebo) injections and will not be asked to return to the clinical study center specifically to receive these injections. Subject (or caregiver) training on this self-injection will take place at Day 1 and can be repeated as required.

For those subjects not entering the LTE, a follow-up visit will be completed at Post Treatment Week 4.

To enhance the safety monitoring during the study, a data monitoring committee (DMC) consisting of independent experts will be convened to periodically review the accumulating safety data for the study. In addition, a cardiovascular safety endpoint adjudication committee (CV-SEAC) will be convened to periodically review and adjudicate all possible major cardiovascular events (MACE).

The assessments planned to be performed at each visit are detailed in the study procedures table ([Appendix 2](#)). A schedule of the study design is provided below.

Figure 3-1. Study Design

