3.8.2. Analysis Visit Windows

Subject visits may not occur on protocol-specified days. Therefore, for the purpose of analysis, observations will be assigned to analysis windows.

In general, the baseline value will be the last nonmissing value on or prior to the first dose date of study drug, except for the mTSS baseline value. The mTSS baseline value will be derived based on the measurements collected on or prior to the first dose date of study drug + 14 days given the potential delay in scheduling an x-ray assessment. If multiple valid, nonmissing measurements exist in the analysis window as aforementioned, in general, the last nonmissing mTSS value on or prior to the first dose date of study drug will be selected as the baseline value; If all these multiple measurements occur at post first dosing, the value closest to the first dose date will be selected as the baseline value.

For subjects who were on placebo and then re-randomized, the baseline after Week 24 will be the last nonmissing value obtained on or prior to the first dose date of filgotinib, except for the mTSS baseline value. The mTSS baseline value will be derived based on the measurements collected on or prior to the first dose date of filgotinib + 14 days given the potential delay in scheduling an x-ray assessment. If multiple valid, nonmissing measurements exist in the analysis window as aforementioned, in general, the last nonmissing mTSS value on or prior to the first dose date of filgotinib will be selected as the baseline value; If all these multiple measurements occur at post first dosing of filgotinib, the value closest to the first dose date of filgotinib will be selected as the baseline value.

For efficacy endpoints, vital signs, ECG, weight, lipids and safety laboratory data, the analysis visit windows will be applied to data collected during the ‘on-treatment’ period. The ‘on-treatment’ period is defined as the last dose date of any study drug + 7 days.

The analysis windows for on-treatment efficacy endpoints including joint count assessment, HAQ-DI (including subject’s pain assessment), subject’s global assessment (SGA), physician’s global assessment (PGA), serum CRP , exploratory patient reported outcome (PRO), and vital signs, weight, and safety laboratory data (lipid data excluded) are provided in [Table 3-1](#) and [Table 3-2](#).

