6.2.1. Definition of the Primary Efficacy Endpoint

A subject achieves ACR20 response when this subject has

- $\geq 20\%$ improvement from baseline in TJC68, AND
- $\geq 20\%$ improvement from baseline in SJC66, AND
- $\geq 20\%$ improvement from baseline in at least 3 of the following 5 items:
 - 1) PGA
 - 2) SGA
 - 3) Subject’s pain assessment
 - 4) HAQ-DI score
 - 5) hsCRP

Percent improvement from baseline at a postbaseline visit is calculated as follows for all 7 components mentioned above:

$$\% \text{ improvement} = \frac{\text{baseline value} - \text{postbaseline value}}{\text{baseline value}} \times 100$$

If the baseline value is 0 then the percent improvement from baseline is set to missing.

In the case that some ACR20 components are missing, the ACR20 assessment will be based on the non-missing components. If non-missing components are not sufficient to determine ACR20 response, then the ACR20 response will be considered as missing.

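### For placebo subjects switched to filgotinib, the SAP's general baseline reset at Week 24 conflicts with the protocol's Day 1 reference for loss of response and leaves ACR-type response after the switch open to two opposite derivations

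*SAP*

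**What the plan says.** Protocol 3.2 sets the loss-of-response criterion against Day 1: "Subjects failing to maintain at least a 20% improvement from Day 1 in TJC and SJC", confirmed at two consecutive visits. The protocol synopsis and the notes to its study procedures table (Appendix 2) say the same.

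The SAP restates the criterion in 1.2 with Baseline in place of Day 1. In 6.1 it turns the criterion into a data rule for nominal Weeks 30 to 52: "For subjects who failed to maintain at least a 20% improvement from Baseline in SJC66 and TJC68", with the result that "efficacy data collected after the second consecutive visit will be excluded from the primary analyses".

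SAP 3.8.2 gives placebo subjects who are re-randomized a second baseline: "the baseline after Week 24 will be the last nonmissing value obtained on or prior to the first dose date of filgotinib". The sentence goes on to treat mTSS separately, with a reset of its own that allows films up to 14 days after the first filgotinib dose.

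For ACR20, SAP 6.2.1 says "Percent improvement from baseline at a postbaseline visit is calculated as follows for all 7 components mentioned above", and "If the baseline value is 0 then the percent improvement from baseline is set to missing". SAP 6.4.1.1 carries this over to ACR50 and ACR70. SAP 6.1 adds: "For all binary response measurements, starting from OC, all missings will be set as non-responders".

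SAP 6.5, which lists the changes from the protocol's efficacy analyses, does not mention a new reference point for loss of response.

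**The concern.** Every visit at which loss of response is judged falls after the switch. That is the period for which 3.8.2 defines a new baseline. No efficacy section says that Day 1 is kept for switchers.

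Subjects who fail the Week 14 joint-count criterion are to stop study drug, and SAP 6.1 drops the later efficacy data of those who continue regardless. Switchers therefore generally reach Week 24 already improved. If the reset applies, keeping a 20% improvement means improving by a further 20% in both joint counts. A subject who simply stays well would lose data from the primary efficacy dataset while the protocol's own criterion keeps that subject on drug.

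ACR20/50/70, ACR-N, EULAR response and HAQ-DI response through Week 52 are listed secondary endpoints (SAP 6.4), and the two switch groups are separate reporting columns (SAP 3.2). Two programmers working from this text could produce opposite results for those columns.

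**Working it through.** The plan gives no figure to reproduce here. The check applies the SAP 6.2.1 formula, (baseline − postbaseline) / baseline × 100, to the same counts under each candidate baseline.

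**1. Stable, well-controlled switcher (illustrative counts).** TJC68/SJC66 is 20/14 on Day 1, 4/2 at Week 24 and 4/2 at every later visit.

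| Reference | TJC68 | SJC66 |
|---|---|---|
| Day 1 | (20 − 4)/20 = 80% | (14 − 2)/14 = 86% |
| Week 24 reset | (4 − 4)/4 = 0% | (2 − 2)/2 = 0% |

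Against Day 1, response is maintained and nothing is excluded. Against the reset, Weeks 30 and 36 both fail, so loss is confirmed at Week 36 and Weeks 44 and 52 are excluded. ACR20 fails on observed data at Weeks 26, 30 and 36. It is missing at Weeks 44 and 52 and is imputed as non-response.

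**2. Entry-minimum counts.** With 6/6 on Day 1 and 1/1 held from Week 24, improvement is (6 − 1)/6 = 83.3% in both counts against Day 1 and 0% against the reset.

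**3. Zero count at Week 24.** If SJC66 or TJC68 is 0, percent improvement is set to missing. ACR20 needs at least 20% improvement in both counts, so it cannot be met at any of the five later visits (Weeks 26, 30, 36, 44, 52), even if the count stays at 0. For the loss-of-response rule the status is then undetermined, so exclusion of data is not certain.

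**4. Other baseline-dependent endpoints.** A switcher at DAS28(CRP) of 3.2 or below who holds steady has an improvement of no more than 0.6 from the reset, which is No Response in SAP Table 6-2. A Week 24 HAQ-DI below 0.22 cannot fall by 0.22, because the scale ends at 0. The cut-offs DAS28(CRP) ≤ 3.2 and < 2.6 use no baseline and are touched only through excluded visits.

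**5. Sensitivity to further improvement.** A simulation assumed SJC66/TJC68 of 15/24 on Day 1, Week 24 means of 3/5 or 6/9, and independent Poisson variation between visits. None of these inputs is in the documents. The share of switchers with Week 52 data excluded was:

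| Further reduction after Week 24 | Reset, means 3/5 | Reset, means 6/9 | Day 1, both cases |
|---|---|---|---|
| none | 76% | 86% | 0% |
| 30% | 54% | 55% | 0% |
| 50% | 34% | 27% | 0% |
| 70% | 16% | 7% | 0% |

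The range of 7% to 86% shows that the choice of baseline matters. It is not an estimate for this trial.

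**6. Week 52 radiographic comparisons.** SAP 6.4.2 compares switchers with continuous filgotinib on change in mTSS and on non-progression. With the mTSS reset, change covers about 52 − 24 = 28 weeks in switchers and 52 weeks in the continuous arms. SAP Table 3-6 agrees: Week 52 is on-filgotinib day 197, and (197 − 1)/7 = 28.

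**The case against.** The strongest reply is that Baseline in SAP 6.1 simply means Day 1, and much of the text supports this.

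- SAP 1.2 swaps Day 1 for Baseline in the Week 14 rule as well, where only Day 1 is possible.
- SAP 6.1 uses the same word for the Week 14 and the Week 30 to 52 rules within one list.
- A subject cannot maintain an improvement from a point at which improvement is zero by construction.
- SAP Table 3-2, which covers switchers' joint counts, HAQ-DI and CRP, has a single Baseline row at study day 1.
- Where the SAP clearly applies the second baseline it names it as such, and it does so in safety sections (7.2, 7.2.2.1, 7.2.2.2, 7.3).

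This stands as evidence of intent, and Day 1 was probably meant. It does not cancel 3.8.2. That sentence is general and covers mTSS, an efficacy measure. If it concerned safety data only, the separate resets for laboratory values, vital signs and weight in section 7 would make it largely redundant.

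The points about scope also stand. SAP 6.4.2 plans no formal testing after Week 24 unless specified, and the switcher tests it specifies are radiographic. Excluded visits remain in the all-available-data set used for the treatment-policy estimand, although that set does not settle which baseline ACR uses. Switchers who improve by a further 20% in both counts escape: a move from 4/2 to 3/1 is 25% and 50%.

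**Conclusion.** The concern holds as a conflict between stated rules. SAP 3.8.2 read with 6.1 and 6.2.1 gives one answer, and the protocol with the rest of the SAP gives another. Applied literally, the SAP would score stable, well-controlled switchers as failures and drop some of their on-drug visits from the primary efficacy dataset.

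A reader might infer more than the documents support:

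- *That the SAP definitely applies the reset to these efficacy rules.* No efficacy section says so. It follows only because 3.8.2 gives the sole definition of a baseline after Week 24.
- *That 200 to 290 subjects would be misclassified.* Taking 45% to 65% of 450 gives 203 to 293, but the re-randomized fraction is an assumption, and the product counts subjects exposed to the wording. The ceiling on exposure is 450, about 225 per dose. The number misclassified cannot be derived.
- *That the main conclusions are at risk.* The primary endpoint and all 19 steps of the hierarchy are at Week 12 or Week 24 and are unaffected.

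The effect is confined to post-Week 24 results of the two placebo-switch groups, which are mostly descriptive. It should still be corrected, because it concerns listed secondary endpoints and can reverse a subject's result.

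**What to change.** - **SAP 6.1, data-exclusion rule for Weeks 30 to 52:** define the reference as the last value before the first dose of any study drug (Day 1), which matches the protocol.
- **SAP 3.8.2:** state that ACR20/50/70, ACR-N, EULAR response and HAQ-DI response for switchers after Week 24 use the Day 1 baseline. Change from the switch can be a supplementary summary.
- **SAP 6.4.2, Week 52 mTSS and non-progression comparisons:** state separately which baseline switchers use, and acknowledge the interval of about 28 versus 52 weeks if the reset is kept. Limiting the reset to safety variables across the board is not the remedy, because it would silently cancel the mTSS reset.
- **Stopping criterion:** SAP 1.2 (Baseline) and the protocol (Day 1) must be reconciled.
- **SAP 6.5:** if any departure from Day 1 is intended for loss of response, list it there.

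The cost is SAP wording and a derivation flag. No new data are needed.

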1.3. Sample Size and Power

Sample size is determined based on the superiority test of filgotinib 200 mg compared to placebo based on the change from Baseline in mTSS at Week 24. When assuming a difference of 0.4 between filgotinib and placebo on change from Baseline in mTSS at Week 24 and a common standard deviation of 1.85, 450 subjects in each of the filgotinib 200 mg group and placebo control group are required to obtain 90% power at a 2-sided 0.05-level.

A sample size of 450 subjects in each of the filgotinib groups and placebo control group will provide over 95% power to detect an increase in ACR20 response rate of 45% to 65% between the placebo control group and the filgotinib group respectively, using a 2-sided 0.05-level test.

Based on {Liu 2014}, 450 subjects in each of the filgotinib 200 mg group and placebo group, and 300 subjects in the adalimumab group, will provide over 90% power at 2-sided 0.05 significance level to demonstrate that filgotinib 200 mg preserves more than 50% of the effect of adalimumab with respect to the response rate of DAS28(CRP) ≤ 3.2 at Week 12, assuming both filgotinib 200 mg and adalimumab groups have similar response rates of DAS28(CRP) ≤ 3.2 . Given this study has a placebo group, assay sensitivity can be established through a direct comparison of adalimumab to placebo.

In summary, the total planned sample size will be 1650 (450 for the filgotinib 200 mg, filgotinib 100 mg, placebo groups, and 300 for the active comparator group).

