6.2.4.2. Missing Data Imputation Analyses

To evaluate the impact of missing data on the ACR20 response rate at Week 12, the following missing value imputation methods will be used:

- The analysis specified in Section 6.2.3 will be performed by using OC and LOCF methods as described in Section 6.1.
- Multiple imputation (MI): The MI procedure replaces each missing binary ACR20 value with a set of plausible values that represent the uncertainty about the right value to impute. Twenty imputed datasets will be generated based on logistic regression models with starting seed 12345. These multiple imputed data sets are then analyzed by using the same method for the primary analysis for complete data as specified in Section 6.2.3. The results from each set of imputed data sets will then be combined using Rubin's rule {Rubin 1987}. The stratification factors will be included in the imputation model as covariates and data at post-baseline visits up to the time point of interest will be included in the longitudinal model.

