 - 2) MI: All subjects with baseline measurement will be included. The MI procedure replaces each missing composite DAS28(CRP) value with a set of plausible values that represent the uncertainty about the right value to impute. Baseline value and stratification factors will be included in the imputation model as covariates, and data at baseline and post-baseline visits up to the time point of interest will be included in the longitudinal model. The multiple imputed datasets will be generated. These multiple imputed data sets are then used to identify subjects with DAS28(CRP) < 2.6 at Week 12, and analyzed by using the analysis method specified in Section 6.3.2 for complete data. The results from each set of imputed data sets will then be combined using Rubin's rule {Rubin 1987}.
 - 3) Tipping point analysis: Similar modified tipping point method as described in Section 6.2.4.2 will be applied to DAS28(CRP) < 2.6 response rate at Week 12.

- Change from Baseline in mTSS at Week 24
 - 1) MI: Similar MI procedure used for analyzing the change from Baseline in HAQ-DI score at Week 12 will be performed.
 - 2) Tipping point analysis: Similar tipping point analysis method used for analyzing the change from Baseline in HAQ-DI score at Week 12 will be performed.
- Non-inferiority analysis of the proportion of subjects who achieve $\text{DAS28(CRP)} \leq 3.2$ or $\text{DAS28(CRP)} < 2.6$ at Week 12
 - 1) The non-inferiority analysis using the same test specified in Section 6.3.2 will be performed by using OC and LOCF methods as described in Section 6.1.
 - 2) MI: Similar MI procedure used for superiority test of the proportion of subjects who achieve $\text{DAS28(CRP)} < 2.6$ at Week 12 will be performed. The multiple imputed data sets will be analyzed by using the non-inferiority analysis specified in Section 6.3.2 for complete data. The results from each set of imputed data sets will then be combined.
 - 3) Tipping point analysis: Similar modified tipping point method as described in Section 6.2.4.2 will be applied to $\text{DAS28(CRP)} \leq 3.2$ or $\text{DAS28(CRP)} < 2.6$ response rate at Week 12. The non-inferiority analysis specified in Section 6.3.2 will be applied when analyzing adjusted data generated under the different δ values.
- Change from Baseline in SF-36 PCS at Week 12
 - 1) MI: Similar MI procedure used for analyzing the change from Baseline in HAQ-DI score at Week 12 will be performed.

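### For subjects who stopped study drug, the OC, LOCF and MI sensitivity analyses of the binary composite estimand answer a different question, because the SAP does not separate drug stops from other missing values

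*SAP*

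**What the plan says.** SAP 6.1 makes the composite estimand primary. For a subject who stops study treatment, or takes standard of care after inadequate response, the rule is to "treat data as missing from the point of inadequate response or study drug discontinuation". The estimand text does not itself call this failure. Failure enters one step later: the primary binary analysis counts missing values as non-response, and the NRI definition covers every missing value whatever its cause.

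The SAP then continues: "To handle the missing data caused by the intercurrent events, the following analyses will be performed for both estimands". For binary endpoints it lists four sensitivity methods.

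- **OC** (6.1): the value stays missing, so the subject leaves the analysis.
- **LOCF** (6.1): the last post-baseline components are carried to the missing visit and the composite is computed from them.
- **MI** (6.2.4.2): "The MI procedure replaces each missing binary ACR20 value with a set of plausible values".
- **Tipping point** (6.2.4.2, Appendix 6): imputation starts under missing at random (MAR), then active-arm values are made worse and placebo values better in steps. The macro selects the records to shift by arm only.

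For the adalimumab comparison, 6.3.3.2 adds: "The non-inferiority analysis using the same test specified in Section 6.3.2 will be performed by using OC and LOCF methods", and then MI and tipping point. Section 6.4.2 uses OC and LOCF for the other binary secondary endpoints, including Week 24. None of these sections separates missing values by reason.

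**The concern.** Under a composite strategy for a binary endpoint, stopping drug is itself the unfavourable outcome, so nothing about that subject is unknown. The SAP carries this out by deleting the value and letting NRI fill in failure. That mixes the intercurrent-event strategy with the missing-data method. When NRI is replaced by OC, LOCF or MI, the failure status of drug-stop subjects goes with it.

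Section 6.2.4.2 says these analyses are there to show the impact of missing data. For drug-stop subjects they vary the estimand instead. OC reports response among those still assessed on drug, MI reports response as if drug had continued, and LOCF reports the last status on drug. A reader of the study report could take agreement with NRI as support for the composite result, or disagreement as a missing-data problem. Neither would follow for these subjects. This matters most for the non-inferiority tests, where a difference between arms in drug stops is part of the composite comparison.

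**Working it through.** **1. The plan's own figures.** SAP 1.3 states that "450 subjects in each of the filgotinib groups and placebo control group will provide over 95% power" for ACR20 at 45% against 65%, "using a 2-sided 0.05-level test". With a pooled two-proportion test:

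- null SE = √(2 × 0.55 × 0.45/450) = 0.0332
- alternative SE = √((0.65 × 0.35 + 0.45 × 0.55)/450) = 0.0325
- power = Φ((0.20 − 1.96 × 0.0332)/0.0325) = 99.998%

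The claim holds. The plan gives no drug-stop rate, so every stop share below is an assumption.

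**2. Who is affected at Week 12.** On-treatment data run to last dose + 7 days (SAP 3.8.2), and the Week 12 window for joint counts and CRP is Day 72 to 92 (Table 3-1). Since 72 − 7 = 65, a last dose before Day 65 leaves no on-treatment Week 12 value. A subject who stops on Day 68 and is assessed on Day 74 keeps an observed value. In what follows, m is the share with no value because of a drug stop.

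**3. Within one arm.** Let p be the NRI rate.

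- OC rate = p/(1 − m). MI under MAR gives the same rate if only arm and strata inform the imputation; earlier visits in the model can lower it.
- LOCF rate = p + m × l, where l is the share of stoppers whose last on-drug status was response.

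None of these is below p, so within an arm the rate can only match or rise.

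**4. Between arms, ACR20.** Take the planning rates of 65% and 45% as NRI rates (difference 20.0 points).

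| m, filgotinib / placebo | OC rates | OC difference |
|---|---|---|
| 10% / 10% | 72.2% / 50.0% | 22.2 points |
| 20% / 5% | 81.3% / 47.4% | 33.9 points |
| 5% / 20% | 68.4% / 56.3% | 12.2 points |

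LOCF with l = 0 leaves 20.0 points in every row.

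**5. Non-inferiority, DAS28(CRP) ≤ 3.2.** Assume on-drug rates of 50/50/25% for filgotinib (T), adalimumab (C) and placebo (P), and no other missing values. Composite rate = on-drug rate × (1 − m). Retention = (T − P)/(C − P). The test statistic is that of SAP 6.3.2:

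Z = (T − 0.5C − 0.5P)/√(T(1−T)/n_T + 0.25 C(1−C)/n_C + 0.25 P(1−P)/n_P)

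The composite analysis uses n = 450/300/450. OC uses the on-drug rates with each n multiplied by (1 − m).

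| Stops T/C/P | Composite T/C/P | Composite retention, Z | OC n | OC retention, Z |
|---|---|---|---|---|
| 10/5/8% | 45.0/47.5/23.0% | 90%, 3.33 | 405/285/414 | 100%, 4.06 |
| 15/5/8% | 42.5/47.5/23.0% | 80%, 2.49 | 382.5/285/414 | 100%, 3.98 |
| 5/10/8% | 47.5/45.0/23.0% | 111%, 4.61 | 427.5/270/414 | 100%, 4.10 |

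In row 2, for example, the composite Z is 0.0725/0.02914 = 2.49 and the OC Z is 0.125/0.03140 = 3.98. OC gives 100% in every row whatever the stop shares, so differences between arms in drug stops have left the comparison. Row 3 shows OC being the harder test.

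**6. Effect of the fix.** Return to step 4 and suppose that 3% of each arm is missing for other reasons, as part of m, and only those are imputed, at the observed rate p/(1 − m). The 10%/10% case becomes (0.65 + 0.03 × 0.722) − (0.45 + 0.03 × 0.500) = 20.7 points. The 20%/5% case gives 21.0 and the 5%/20% case 20.4. The analysis now moves only with the values that are truly unknown.

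**The case against.** Much of the plan speaks against a wider criticism.

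- **A reader might infer that these analyses cannot test the primary result at all.** The documents do not support that. NRI also covers missed visits, ACR20 with insufficient components (6.2.1) and DAS28(CRP) with any missing component (6.3.1.1). For those values OC, LOCF and MI are proper checks.
- **Further checks exist.** The tipping point can be stricter than the primary analysis. If all missing filgotinib values fail and all missing placebo values respond, the 20-point difference falls to 10 points (p = 0.002) with 10% missing per arm and to 5 points (p = 0.12) with 15%. The treatment-policy estimand uses observed data after a drug stop, and the protocol (3.2, 3.5.2) keeps such subjects in study visits or encourages them to stay. Section 6.2.3 counts non-responders due to missing by arm, and 4.1 tabulates discontinuation reasons by arm.
- **A reader might infer that the arm with most stops always gains most.** That is true for OC only in relative terms. In points, 10% missing on filgotinib and 12% on placebo lifts filgotinib by 7.2 and placebo by 6.1. For LOCF the gain depends on last on-drug status. Nor do the documents say which arm will have most stops.
- **Scope.** Every binary test in the hierarchy is at Week 12, before the Week 14 inadequate-response rule acts.

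All of this stands and limits the point. It does not supply the missing rule: no section keeps drug-stop subjects as failures under OC, LOCF or MI, and the tipping point also begins by imputing them under MAR.

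**Conclusion.** The point holds for a defined group: subjects whose on-treatment value is missing because they stopped study drug. For them, OC, LOCF and MI on the composite dataset change the question, so agreement with NRI is not evidence of robustness to missing data.

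The size cannot be fixed from the documents, which give no stop rates. Under the assumed rates above, retention moves from 80% to 100% in one case and from 111% to 100% in another, so the direction depends on response rates and stop shares by arm. In all three non-inferiority illustrations Z exceeds 1.96 under both analyses, so the conclusion does not change there.

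The primary test, the testing hierarchy and type I error are untouched, and the SAP does not let a sensitivity analysis override the primary result. The inadequate-response rule adds to the problem only for later binary endpoints such as those at Week 24. This should be corrected because the supportive analyses would otherwise be misread, and the correction is cheap.

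**What to change.** In SAP 6.1, 6.2.4.2, 6.3.3.2 and 6.4.2, add one rule for binary endpoints under the composite estimand:

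- Subjects whose value is missing because of study drug discontinuation or inadequate response stay non-responders in every sensitivity analysis.
- OC, LOCF, MI and tipping point apply only to values missing for other reasons. The Appendix 6 macro then needs a reason flag as well as the arm.
- The present versions, if wanted, are kept and labelled as supplementary analyses of a different estimand.
- Missing values are tabulated by reason and arm, extending the count already planned in 6.2.3.

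The cost is one derived flag, from last-dose dates and discontinuation reasons already collected, and a few more tables.
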